10.3.3 Definition of Product Complaints

Product Complaint

- A PC is any written, electronic, or oral communication that alleges deficiencies related to the identity, quality, durability, reliability, safety, effectiveness or performance of a study intervention. When the ability to use the study intervention safely is impacted, the following are also PCs:
 - Deficiencies in labeling information, and
 - Use errors for device or drug-device combination products due to ergonomic design elements of the product.
- Product complaints related to study interventions used in clinical trials are collected in order to ensure the safety of participants, monitor quality, and to facilitate process and product improvements.
- Investigators will instruct participants to contact the site as soon as possible if he/she has a PC or problem with the study intervention so that the situation can be assessed.
- An event may meet the definition of both a PC and an AE/SAE. In such cases, it should be reported as both a PC and as an AE/SAE.

10.3.4 Recording and Follow-Up of AE and/or SAE and Product Complaints

AE, SAE, and Product Complaint Recording

- When an AE/SAE/PC occurs, it is the responsibility of the investigator to review all documentation (e.g., hospital progress notes, laboratory reports, and diagnostics reports) related to the event.
- The investigator will then record all relevant AE/SAE/PC information in the participant's medical records, in accordance with the investigator's normal clinical practice. AE/SAE information is reported on the appropriate CRF page and PC information is reported on the Product Complaint Form.

Note: An event may meet the definition of both a PC and an AE/SAE. In such cases, it should be reported as both a PC and as an AE/SAE.

- It is **not** acceptable for the investigator to send photocopies of the participant's medical records to Sponsor or designee in lieu of completion of the CRF page for AE/SAE and the Product Complaint Form for PCs.
- There may be instances when copies of medical records for certain cases are requested by Sponsor or designee. In this case, all participant identifiers, with the exception of the participant number, will be redacted on the copies of the medical records before submission to Sponsor or designee.
- The investigator will attempt to establish a diagnosis of the event based on signs, symptoms, and/or other clinical information. Whenever possible, the diagnosis (not the individual signs/symptoms) will be documented as the AE/SAE.

Assessment of Intensity

The investigator will make an assessment of intensity for each AE and SAE reported during the study and assign it to one of the following categories:

- Mild: A type of AE that is usually transient and may require only minimal treatment or therapeutic intervention. The event does not generally interfere with usual activities of daily living.
- Moderate: A type of AE that is usually alleviated with additional specific therapeutic intervention. The event interferes with usual activities of daily living, causing discomfort but poses no significant or permanent risk of harm to the research participant.
- Severe: A type of AE that interrupts usual activities of daily living, or significantly affects clinical status, or may require intensive therapeutic intervention. An AE that is assessed as severe should not be confused with an SAE. Severe is a category utilized for rating the intensity of an event; and both AEs and SAEs can be assessed as severe.

An event is defined as "serious" when it meets at least one of the predefined outcomes as described in the definition of an SAE, NOT when it is rated as severe.

Assessment of Causality

- The investigator is obligated to assess the relationship between study intervention and each occurrence of each AE/SAE. The investigator will use clinical judgment to determine the relationship.
- A “reasonable possibility” of a relationship conveys that there are facts, evidence, and/or arguments to suggest a causal relationship, rather than a relationship cannot be ruled out.
- Alternative causes, such as underlying disease(s), concomitant therapy, and other risk factors, as well as the temporal relationship of the event to study intervention administration will be considered and investigated.
- The investigator will also consult the IB in his/her assessment.
- For each AE/SAE, the investigator **must** document in the medical notes that he/she has reviewed the AE/SAE and has provided an assessment of causality.
- There may be situations in which an SAE has occurred and the investigator has minimal information to include in the initial report to Sponsor or designee. However, it is very important that the investigator always make an assessment of causality for every event before the initial transmission of the SAE data to Sponsor or designee.
- The investigator may change their opinion of causality in light of follow-up information and send an SAE follow-up report with the updated causality assessment.
- The causality assessment is one of the criteria used when determining regulatory reporting requirements.

Follow-up of AEs and SAEs

- The investigator is obligated to perform or arrange for the conduct of supplemental measurements and/or evaluations as medically indicated or as requested by Sponsor or designee to elucidate the nature and/or causality of the AE or SAE as fully as possible. This may include additional laboratory tests or investigations, histopathological examinations, or consultation with other healthcare professionals.
- If a participant dies during participation in the study or during a recognized follow-up period, the investigator will provide Sponsor or designee with a copy of any postmortem findings including histopathology.
- New or updated information will be recorded in the originally completed eCRF.
- The investigator will submit any updated SAE data to the Sponsor or designee within 24 hours of receipt of the information.

10.3.5 Reporting of SAEs

SAE Reporting via an Electronic Data Collection Tool

- The primary mechanism for reporting an SAE will be the electronic data collection tool.
- If the electronic system is unavailable or if a pregnancy is reported, then the site will use the paper SAE or pregnancy data collection tool (see next section) to report the event within 24 hours.
- The site will enter the SAE data into the electronic system as soon as it becomes available.
- After the study is completed at a given site, the electronic data collection tool will be taken offline to prevent the entry of new data or changes to existing data.
- If a site receives a report of a new SAE from a study participant or receives updated data on a previously reported SAE after the electronic data collection tool has been taken offline, then the site can report this information on a paper SAE form (see next section) or to the Sponsor or designee by telephone.
- Contacts for SAE reporting can be found in the site training documents.

SAE Reporting via Paper Form

- In the event the electronic system is unavailable, facsimile transmission of the SAE paper CRF is the preferred method to transmit this information to the Sponsor.
- Initial notification via telephone does not replace the need for the investigator to complete and sign the SAE CRF pages within the designated reporting time frames.
- Contacts for SAE reporting can be found in the site training documents

10.3.6 Regulatory Reporting Requirements

SAE Regulatory Reporting

- Prompt notification by the investigator to the Sponsor of an SAE is essential so that legal obligations and ethical responsibilities towards the safety of participants and the safety of a study intervention under clinical investigation are met.
- The Sponsor has a legal responsibility to notify both the local regulatory authority and other regulatory agencies about the safety of a study intervention under clinical investigation. The Sponsor will comply with country-specific regulatory requirements relating to safety reporting to the regulatory authority, IRB/IEC, and investigators.
- An investigator who receives an investigator safety report describing an SAE or other specific safety information (e.g., summary or listing of SAEs) from the Sponsor will review and then file it along with the Investigator's Brochure and will notify the IRB/IEC, if appropriate, according to local requirements.

10.4 Appendix 4: Contraceptive and Barrier Guidance

10.4.1 Definitions

Woman of Childbearing Potential (WOCBP)

A woman is considered fertile following menarche and until becoming post-menopausal unless permanently sterile (see below).

If fertility is unclear (e.g., amenorrhea in adolescents or athletes) and a menstrual cycle cannot be confirmed before first dose of study intervention, additional evaluation should be considered.

Women in the following categories are not considered WOCBP:

- Premenarchal
- Premenopausal female with 1 of the following:
 - Documented hysterectomy
 - Documented bilateral salpingectomy
 - Documented bilateral oophorectomy

For individuals with permanent infertility due to an alternate medical cause other than the above, (e.g., Mullerian agenesis, androgen insensitivity), investigator discretion should be applied to determining study entry.

Note: Documentation can come from the site personnel's: review of the participant's medical records, medical examination, or medical history interview.

A postmenopausal female is defined as women with:

- At least 6 weeks post-surgical bilateral oophorectomy with or without hysterectomy, confirmed by operative note.

OR

- With spontaneous amenorrhea for at least 12 months, not induced by a medical condition such as anorexia nervosa and not taking medications during the amenorrhea (e.g., oral contraceptives, hormones, gonadotropin releasing hormone, anti-estrogens, selective estrogen receptor modulators (SERMs), or chemotherapy that induced the amenorrhea. And if age ≤ 50 , has an FSH of ≥ 40 mIU/mL and estradiol of ≤ 30 pg/mL.

Contraception guidance for women of childbearing potential (WOCBP):

See Section 5.1, inclusion criterion [1b].

Contraception guidance for men:

See Section 5.1, inclusion criterion [1a].

10.4.2 Contraception Guidance

Male participants with partners who become pregnant

The investigator will attempt to collect pregnancy information on a male participant's female partner who becomes pregnant while the male participant is in this study.

After obtaining the necessary signed informed consent and/or assent from the pregnant female partner directly, the investigator will record pregnancy information on the appropriate form and submit it to the Sponsor within 24 hours of learning of the partner's pregnancy. The female partner will also be followed up to determine the outcome of the pregnancy. Information on the status of the mother and child will be forwarded to the Sponsor. Generally, the follow-up will be no longer than 6 to 8 weeks following the estimated delivery date. Any termination of the pregnancy will be reported, including fetal status (presence or absence of anomalies) or indication for the procedure.

Female participants who become pregnant

The investigator will collect pregnancy information on any female participant who becomes pregnant while participating in this study. The initial information will be recorded on the appropriate form and submitted to the Sponsor within 24 hours of learning of a participant's pregnancy.

The participant will be followed up to determine the outcome of the pregnancy. The investigator will collect follow-up information on the participant and the neonate, and the information will be forwarded to the Sponsor. Generally, follow-up will not be required for longer than 6 to 8 weeks beyond the estimated delivery date. Any termination of pregnancy will be reported, including fetal status (presence or absence of anomalies) or indication for the procedure.

While pregnancy itself is not considered to be an AE or SAE, any pregnancy complication or elective termination of a pregnancy for medical reasons will be reported as an AE or SAE.

A spontaneous abortion (occurring at <20 weeks gestational age) or still birth (occurring at ≥20 weeks gestational age) is always considered to be an SAE and will be reported as such.

Any post-study pregnancy-related SAE considered reasonably related to the study intervention by the investigator will be reported to the Sponsor. While the investigator is not obligated to actively seek this information in former study participants, the investigator may learn of an SAE through spontaneous reporting.

Any female participant who becomes pregnant while participating in the study will permanently discontinue the study intervention (see Section 7.1.1).

10.5 Appendix 5: Liver Safety: Suggested Actions and Follow-Up Assessments

See Section 8.2.8.1 for guidance on appropriate test selection.

The Lilly-designated central laboratory must complete the analysis of all selected testing except for microbiology testing.

Local testing may be performed in addition to central testing when necessary for immediate participant management.

Results will be reported if a validated test or calculation is available.

Hematology	Clinical Chemistry
Hemoglobin	Total bilirubin
Hematocrit	Direct bilirubin
Erythrocytes (RBCs – red blood cells)	Alkaline phosphatase (ALP)
Leukocytes (WBCs – white blood cells)	Alanine aminotransferase (ALT)
Differential:	Aspartate aminotransferase (AST)
Neutrophils, segmented	Gamma-glutamyl transferase (GGT)
Lymphocytes	Creatine kinase (CK)
Monocytes	Other Chemistry
Basophils	Acetaminophen
Eosinophils	Acetaminophen protein adducts
Platelets	Alkaline phosphatase isoenzymes
Cell morphology (RBC and WBC)	Ceruloplasmin
	Copper
Coagulation	Ethyl alcohol (EtOH)
Prothrombin time, INR (PT-INR)	Haptoglobin
Serology	Immunoglobulin A (IgA, quantitative)
Hepatitis A virus (HAV) testing:	Immunoglobulin G (IgG, quantitative)
HAV total antibody	Immunoglobulin M (IgM, quantitative)
HAV IgM antibody	Phosphatidylethanol (Peth)
Hepatitis B virus (HBV) testing:	Urine Chemistry
Hepatitis B surface antigen (HBsAg)	Drug screen
Hepatitis B surface antibody (anti-HBs)	Ethyl glucuronide (EtG)
Hepatitis B core total antibody (anti-HBc)	Other Serology
Hepatitis B core IgM antibody	Anti-nuclear antibody (ANA)
Hepatitis B core IgG antibody	Anti-smooth muscle antibody (ASMA) ^a

Hematology	Clinical Chemistry
HBV DNA ^d	Anti-actin antibody ^b
Hepatitis C virus (HCV) testing:	Epstein-Barr virus (EBV) testing:
HCV antibody	EBV antibody
HCV RNA ^d	EBV DNA ^d
Hepatitis D virus (HDV) testing:	Cytomegalovirus (CMV) testing:
HDV antibody	CMV antibody
Hepatitis E virus (HEV) testing:	CMV DNA ^d
HEV IgG antibody	Herpes simplex virus (HSV) testing:
HEV IgM antibody	HSV (Type 1 and 2) antibody
HEV RNA ^d	HSV (Type 1 and 2) DNA ^d
Microbiology^c	Liver kidney microsomal type 1 (LKM-1) antibody
Culture:	
Blood	
Urine	

^a Not required if anti-actin antibody is tested.

^b Not required if anti-smooth muscle antibody (ASMA) is tested.

^c Assayed ONLY by investigator-designated local laboratory; no central testing available.

^d Reflex/confirmation dependent on regulatory requirements, testing availability, or both.

10.6 Appendix 6: Protocol RHCZ CASPAR Criteria

CASPAR Criteria

The CASPAR criteria for psoriatic arthritis consist of inflammatory articular disease (joint, spine, or enthesseal) with **≥3 points** from the following 5 categories.

- Evidence of current psoriasis, a personal history of psoriasis, or a family history of psoriasis (**2 points**)
 - Current psoriasis is defined as psoriatic skin or scalp disease present today as judged by a rheumatologist or dermatologist.†
 - A personal history of psoriasis is defined as a history of psoriasis that may be obtained from a participant, family physician, dermatologist, rheumatologist, or other qualified healthcare provider.
 - A family history of psoriasis is defined as a history of psoriasis in a first- or second-degree relative according to participant report.
- Typical psoriatic nail dystrophy including onycholysis, pitting, and hyperkeratosis observed on current physical examination (**1 point**)
- A negative test result for the presence of rheumatoid factor by any method except latex (**1 point**)
- Either current dactylitis, defined as swelling of an entire digit, or a history of dactylitis recorded by a rheumatologist (**1 point**)
- Radiographic evidence of juxta-articular new bone formation appearing as ill-defined ossification near joint margins (but excluding osteophyte formation) on plain radiographs of the hand or foot (**1 point**)

† Current psoriasis is assigned a score of 2; all other features are assigned a score of 1.

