- Women who are infertile due to surgical sterilization (hysterectomy, bilateral oophorectomy, or tubal ligation) and congenital anomaly such as Müllerian agenesis.

[3] Have given written informed consent approved by Lilly, or its designee, and the Investigational Review Board (IRB)/ERB governing the site.

[4] Willing to self-administer study intervention.

For PsO Participants

[5] Present with chronic PsO based on a confirmed diagnosis of chronic PsO vulgaris for at least 6 months prior to baseline (Week 0; Visit 2).

[6] Have $\geq 10\%$ BSA of psoriasis at screening (Visit 1) and baseline (Week 0; Visit 2).

[7] Have both an sPGA score of ≥ 3 and PASI score ≥ 12 at screening (Visit 1) and baseline (Week 0; Visit 2).

- [8] Are a candidate for phototherapy and/or systemic therapy.

For PsA Participants

- [9] Have a diagnosis of active PsA for at least 6 months (based on a detailed medical history provided by the patient, and a physical exam by the Study Investigator, and/or other evidence such as that provided by joint x-rays, that establishes a history consistent with a diagnosis of active PsA of at least 6 months' duration) and currently meet the Classification for PsA (CASPAP) criteria (Section 10.6).
- [10] Have active PsA defined as the presence of at least 3/68 tender and at least 3/66 swollen joints, as determined by the Tender and Swollen Joint Count Assessment Form (Section 10.7) at Visit 1 (Screening) and Visit 2 (Week 0, baseline).
- [11] Presence of active PsO or a documented history of psoriasis.

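### Appendix 6 gives two CASPAR scores for a personal history of psoriasis without current psoriasis, which decides eligibility when exactly one other feature is present

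*Protocol*

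**What the plan says.** Protocol Section 10.6 (Appendix 6) classifies psoriatic arthritis as inflammatory articular disease "with ≥3 points from the following 5 categories". The first category reads "Evidence of current psoriasis, a personal history of psoriasis, or a family history of psoriasis" and carries 2 points. The other four categories (nail dystrophy, negative rheumatoid factor, dactylitis, juxta-articular new bone formation) carry 1 point each.

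Three sub-bullets define the terms of the first category. Current psoriasis is one of them: "Current psoriasis is defined as psoriatic skin or scalp disease present today as judged by a rheumatologist or dermatologist". A dagger is attached to that sub-bullet and to neither of the two history sub-bullets. It leads to the footnote: "Current psoriasis is assigned a score of 2; all other features are assigned a score of 1".

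In Protocol Section 5.1, criterion [9] makes Section 10.6 an entry condition for PsA participants. Criterion [11] asks for "Presence of active PsO or a documented history of psoriasis", so a PsA participant need not have skin disease at entry.

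**The concern.** The list and its footnote do not give the same score to a person who has had psoriasis but does not have it today. The list puts that person in a 2-point category. The footnote reserves the score of 2 for current psoriasis and gives 1 to everything else. No other part of the Protocol says which applies.

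CASPAR is an entry criterion, so the choice of line can decide whether a candidate is enrolled. Criterion [11] makes history-only candidates an intended part of the PsA cohort, so the case is not hypothetical. Section 5 does not permit waivers of enrolment criteria. The same person could therefore be properly enrolled at one site, and at another be a screen failure or, if already enrolled, a case for the inadvertent-enrolment procedure in Section 7.2.1.

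**Working it through.** **Inputs**

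- Threshold: at least 3 points (Section 10.6).
- Psoriasis category by the list: 2 points for current disease, personal history or family history (Section 10.6).
- Psoriasis category by the literal footnote: 2 for current disease, 1 for personal or family history (Section 10.6).
- Four other features at 1 point each (Section 10.6).
- Assumption: the psoriasis category is counted once per person.

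**Formula.** Score = psoriasis points + k, where k is the number of other features present (0 to 4). The candidate meets CASPAR if the score is at least 3.

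**Personal history only**

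| k | List: 2 + k | Footnote: 1 + k | Same decision? |
|---|---|---|---|
| 0 | 2, not met | 1, not met | yes |
| 1 | 3, met | 2, not met | **no** |
| 2 | 4, met | 3, met | yes |
| 3 | 5, met | 4, met | yes |
| 4 | 6, met | 5, met | yes |

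Four features, each present or absent, give 2 × 2 × 2 × 2 = 16 patterns. The decision differs in 4 of them, namely those with exactly one feature present. These are patterns, not patients, so 4/16 is not an estimate of how often the conflict will arise.

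**Current psoriasis.** Both lines give 2 + k, so the decision differs in 0 of 16 patterns.

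**Family history only.** The scores are the same as for personal history. On its natural reading, however, criterion [11] requires the participant's own active or past psoriasis. A candidate with only a family history would then fail [11] whatever the CASPAR score, so the practical conflict concerns personal history.

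**Where the affected candidates go.** Section 2.1 defines moderate-to-severe psoriasis as PASI ≥12, sPGA ≥3 and BSA ≥10%. A person with no current psoriasis cannot meet this, so Table RHCZ.6.1 places them on the Q4W/Q4W regimen. That is one of the two regimens by which Section 9.5.5 summarizes safety.

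**Size.** The planned PsA cohort is 100 (Section 9.7), so each 1% of it is 1 participant. The Protocol gives neither the share of PsA candidates without current psoriasis nor the share with exactly one other feature. The number affected cannot be calculated and could be close to zero.

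**The case against.** The strongest reply is that the text does not force a contradiction. No line says outright that a history of psoriasis scores 1. The appendix scores five categories with the points printed beside each. If the footnote is shorthand for that layout, with psoriasis at 2 and the other four categories at 1, it agrees with the list and history scores 2. This reading is possible. It does not explain why the footnote names current psoriasis rather than the psoriasis category, or why the dagger is on the current-psoriasis sub-bullet alone. A site applying the footnote as written would score history as 1, so the ambiguity stands.

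The reply is right on scope. A reader might infer that eligibility flips for every PsA participant without current psoriasis. The arithmetic shows that it flips only with exactly one other feature.

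A reader might also infer that the scoring defines the PsA analysis population and hence the ACR20 denominator. The Protocol does not support this. Section 9.2 builds the Active PsA mITT population from enrolled participants with that indication who received at least one dose, even if they otherwise depart from the protocol. Section 5 and criterion [10] define active PsA by joint counts, not by CASPAR points. A dosed participant whose CASPAR score was misjudged stays in that denominator and in the safety population.

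It is also fair to say that the inferential stakes are low. Section 9.1 plans no hypothesis test, the primary analysis is descriptive safety, and ACR20 is a single-arm proportion with a confidence interval. Nothing in the Protocol shows that a reported result would change materially.

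**Conclusion.** The point holds in a narrow form. Appendix 6 can be read to give a personal history of psoriasis without current disease either 2 points or 1, and nothing else in the Protocol settles it. The choice decides entry for a PsA candidate with personal history only and exactly one other CASPAR feature, and for no one else who satisfies criterion [11].

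The consequence is an entry rule that sites may apply differently. It affects who is screened into the PsA cohort and the Q4W/Q4W safety group. It does not alter the definition of any analysis set.

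The conclusion rests on a literal reading of the footnote, on counting the psoriasis category once, and on the natural reading of [11] as the participant's own history. The number affected is not given. The case for correcting it is that it sits in an eligibility criterion and is cheap to remove, not that a large effect has been shown. This review does not say which score is right.

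**What to change.** Reconcile the category list and the footnote in Appendix 6 with the source the appendix cites. Then print one explicit score each for current psoriasis, personal history and family history, and reword or remove the footnote so that it cannot be read against the list. If sites are already screening, tell them which score applies, and check the entry decisions for PsA candidates with personal history only and exactly one other feature, including screen failures.

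The cost is appendix wording and a short site communication. Sample size, visits, endpoints and analysis sets do not change.
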